#### **16.2.2.4. Analysis of the Primary Endpoint**

The population for the primary endpoint analysis will be subjects in the ITT population with a baseline and at least one post-baseline CDR-SB score. A mixed model repeated measures (MMRM) model will be used as the primary analysis to analyze change from baseline CDR-SB using fixed effects of treatment, time, treatment-by-time interaction, baseline CDR-SB, baseline CDR-SB by time, baseline MMSE, and baseline ApoE  $\epsilon 4$  status.

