## 7. STUDY DESIGN

### 7.1. Study Overview

Study 221AD301 is a multicenter, randomized, double-blind, placebo-controlled, parallel-group study in subjects with early AD, including MCI due to AD and a subset of mild AD, followed by an optional 24-month dose-blind LTE study. Approximately 1350 subjects will be enrolled across approximately 150 centers globally. The primary study objective is to evaluate the efficacy of monthly doses of aducanumab on the CDR-SB relative to placebo. Secondary objectives include assessment of the effect of monthly doses of aducanumab on clinical progression as compared to placebo. The safety of monthly doses of aducanumab will also be evaluated.

Subjects will receive infusions of aducanumab or placebo approximately every 4 weeks for approximately 18 months (a total of 20 doses). Subjects will be randomized to receive aducanumab low dose: aducanumab high dose: placebo in a 1:1:1 ratio. The randomization will be stratified by site and ApoE  $\epsilon$ 4 status (carrier or non-carrier). Subject enrollment will be monitored so that approximately 60% to 70% ApoE  $\epsilon$ 4 carriers are enrolled. Enrollment will also be monitored, via interactive response technology (IRT), such that subjects with mild AD represent a small percentage of the total enrolled in the trial.

At the end of the double-blind, placebo-controlled treatment period, subjects who meet the extension entry criteria may enter a 24-month long-term safety and efficacy extension period, with all subjects receiving aducanumab approximately every 4 weeks (a total of 26 doses).

The total duration of study participation for each subject only participating in the placebo-controlled period of the study will be up to approximately 102 weeks, including a series of Screening visits within 8 weeks before administration of the first dose, a 76-week placebo-controlled treatment period, and a safety follow-up (FU) period of approximately 18 weeks after the final dose.

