### **9.2. Randomization and Registration of Subjects**

Subjects will be registered at the Screening Visit and randomized only after all baseline assessments have been completed and the Investigator has verified that the subjects are eligible per criteria in Sections 8.1 and 8.2. No subject may begin treatment prior to assignment of a unique identification number (registration) and randomization. Any subject identification numbers or randomization schedule assignments that are assigned will not be reused even if the subject does not receive treatment. Rescreened subjects will be assigned a new number.

Subjects will be randomized to receive aducanumab low dose; aducanumab high dose; placebo in a 1:1:1 ratio. The randomization will be stratified by site and ApoE  $\epsilon 4$  status (carrier or non-carrier), so that approximately 60% to 70% ApoE  $\epsilon 4$  carriers are enrolled. Enrollment will also be monitored, via the IRT, such that the population of subjects with mild AD represents a small percentage of the total enrolled in the trial. Subjects who withdraw from the study may not be replaced.

Refer to the Study Reference Guide for details on registration and randomization.

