### **16.7. Sample Size Considerations**

The study's sample size is based, in part, on results from a protocol-specified interim analysis from Study 221AD103 which included 1 year data from 1, 3 and 10 mg/kg treatment groups.

A sample size of 450 subjects per treatment group will have approximately 90% power to detect a true mean difference of 0.5 in change from baseline CDR-SB at Week 78 between the 2 treatment groups. This power calculation is based on a 2-sided t-test assuming equal variance with a final significance level of 0.05, a SD of 1.92 and a drop-out rate of 30%. The SD estimate of 1.92 for Week 78 reflects a 39% increase over the SD from the protocol-specified interim analysis of 1-year data.

The assumed true mean difference of 0.5 between the 2 treatment groups represents an approximately 25% reduction in the placebo mean change from baseline at Week 78 if the placebo mean change is estimated to be 2.

The sample size may be reassessed in a blinded manner approximately 3 months before enrollment is complete if at least 15% of the data are available on the primary endpoint. At this interim time-point, the SD for the primary endpoint will be estimated based on the blinded data. The sample size may be increased if the SD is estimated to be more than approximately 2.07. In addition, the sample size could be increased using external clinical trial results that become available after the start of the study.

CONFIDENTIAL

The information contained herein may not be used, disclosed, or published without the written consent of Biogen MA Inc.

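### The primary MMRM leaves out site, one of the two randomization factors, and holds the ApoE ε4 and baseline MMSE effects constant over visits: a small loss of precision at Week 78 if these terms are prognostic

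*Protocol*

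**What the plan says.** Protocol v3.0, Section 9.2: "The randomization will be stratified by site and ApoE" ε4 status, with three arms in a 1:1:1 ratio. Section 7.1 sets the scale: "Approximately 1350 subjects will be enrolled across approximately 150 centers globally".

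Section 16.2.2.4 fits an MMRM to change from baseline in CDR-SB "using fixed effects of treatment, time, treatment-by-time interaction, baseline CDR-SB, baseline CDR-SB by time, baseline MMSE, and baseline ApoE" ε4 status. There is no site, pooled-site or region term. Baseline CDR-SB has a by-time term; baseline MMSE and ApoE ε4 status are main effects only. Versions 1.0 and 2.0 list the same model.

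The secondary models in Section 16.2.2.5 follow the same pattern: the outcome's own baseline has a by-time term, ApoE ε4 is a main effect, and site is absent. The MMSE model therefore already has baseline MMSE by time; the ADAS-Cog 13 and ADCS-ADL-MCI models carry baseline MMSE as a main effect.

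The sample size in Section 16.7 takes no credit for covariates. It rests on a "2-sided t-test assuming equal variance with a final significance level of 0.05, a SD of 1.92 and a drop-out rate of 30"%.

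**The concern.** Stratifying by a factor balances its prognostic effect across arms. If the analysis then ignores the factor, its variance stays in the residual although the design has largely removed it from the treatment comparison. The model-based standard error is then too large and the test somewhat conservative. Site could plausibly matter here: the scales are rater-administered at about 150 centers worldwide, and the protocol takes care over rater consistency.

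The second part concerns the visits. The endpoint is Week 78 alone, but one ApoE coefficient and one MMSE coefficient must serve every visit. If either effect changes over time, the adjustment at Week 78 is less than fully efficient. The protocol already allows for this with baseline CDR-SB and gives no reason for treating the other two differently.

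At stake is precision in the primary comparison and in the fixed-sequence tests that follow it.

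**Working it through.** **Inputs from v3.0.** 450 subjects per group, difference 0.5, SD 1.92, two-sided alpha 0.05 and 30% dropout (Section 16.7); about 1350 subjects at about 150 centers (Section 7.1); 60% to 70% ApoE ε4 carriers (Section 7.1).

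**Assumptions, not in the documents.** Site ICC from 0 to 0.10. Part of the Week 78 effect missed by the constant coefficient: an ApoE difference of 0.2 to 0.5 points, and an MMSE slope of 0.05 to 0.2 per point with a baseline MMSE SD of 1.5 to 2.0.

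**1. The plan's own figure.** Evaluable per arm: 450 × 0.70 = 315. SE = 1.92 × √(2/315) = 0.153, and 0.5/0.153 = 3.27. Power = Φ(3.27 − 1.96) = 0.905 (0.904 with the t distribution). In reverse, 90% power needs 310 evaluable per arm, and 310/0.70 = 443, against 450 stated. The figure reproduces with no covariate.

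**2. Ceiling for site.** Suppose site explains a share r of the Week 78 variance, is perfectly balanced, and can be removed at no cost. The interval is then too wide by a factor 1/√(1 − r), and the true alpha is 2 × [1 − Φ(1.96/√(1 − r))].

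| r | interval too wide by | true alpha | power without site | power with site |
|---|---|---|---|---|
| 2% | 1.0% | 0.048 | – | 91.0% |
| 5% | 2.6% | 0.044 | 91.0% | 91.8% |
| 10% | 5.4% | 0.039 | 91.6% | 93.1% |

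**3. A more realistic size.** Sites average 1350/150 = 9 randomized subjects, 3 per arm, and 9 × 0.70 = 6.3 evaluable, so neither perfect balance nor free recovery holds. A single-visit simulation used 1500 runs per setting, 150 sites, blocks of 3 within site by ApoE (block size assumed), 30% random dropout, and a known ICC in the random-site fit. Each cell gives the result for equal / unequal site sizes.

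| ICC | mean SE, no site | mean SE, fixed site | mean SE, random site | power, no site | power, fixed site | power, random site |
|---|---|---|---|---|---|---|
| 0 | 0.1530 / 0.1530 | 0.1586 / 0.1590 | 0.1530 / 0.1530 | 0.900 / 0.901 | 0.867 / 0.871 | 0.900 / 0.901 |
| 0.02 | 0.1530 / 0.1532 | 0.1571 / 0.1576 | 0.1521 / 0.1522 | 0.906 / 0.911 | 0.893 / 0.885 | 0.909 / 0.913 |
| 0.05 | 0.1530 / 0.1529 | 0.1546 / 0.1549 | 0.1504 / 0.1501 | 0.894 / 0.904 | 0.886 / 0.891 | 0.900 / 0.911 |
| 0.10 | 0.1533 / 0.1531 | 0.1506 / 0.1509 | 0.1474 / 0.1469 | 0.897 / 0.908 | 0.897 / 0.904 | 0.907 / 0.919 |

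Against the model without site, the random-site SE is smaller by about 0.6% at ICC 0.02 (0.1530 to 0.1521), 1.7 to 1.8% at 0.05, and 4% at 0.10. The power gain runs from 0 to about 1 point; Monte Carlo error on a single power figure is about 0.8 points. Fixed site effects give a larger SE up to ICC 0.05, and power no better than without site at any ICC.

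**4. By-visit terms.** The ApoE term removes a variance share p(1 − p)d²/1.92². The largest value is 0.6 × 0.4 × 0.5²/3.686 = 0.016, which makes the interval at most 0.8% narrower. The MMSE term removes (slope × SD)²/1.92², from (0.05 × 1.5)²/3.686 = 0.0015 to (0.2 × 2.0)²/3.686 = 0.043, an interval about 0.1% to 2.2% narrower.

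**The case against.** The case for leaving the model alone is respectable. The protocol nowhere promises to adjust for every stratification factor, and ApoE ε4 is in the model. With about 6 evaluable subjects per site, omitting site is defensible, and step 3 shows that fitting it as a fixed effect would mostly do harm. No ICC or covariate-by-visit effect is given, and at ICC 0 omitting site costs nothing. Section 16.2.2.4 lists fixed effects only, so it does not rule out a random site effect in the SAP, which is not shown. Section 16.2.2.4 of v4.0 is not shown either.

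Most of this stands. It limits the size and certainty of the point but leaves two facts in place: the protocol spells out its covariate list and includes one randomization factor without the other, and it gives only one baseline covariate a by-time term. No reason is stated for either choice. Elsewhere the protocol says explicitly what it leaves to the SAP, such as the futility criteria and the extension analyses; Section 16.2.2.4 contains no such deferral.

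A reader might infer that the omission biases the treatment effect, inflates type I error or leaves the trial underpowered. The documents support none of these. Randomization and the treatment-by-time term protect the Week 78 contrast, any error in the standard error is on the conservative side, and the stated power assumes no covariate adjustment. Nor can one say that the intervals are too wide as a fact; that depends on site being prognostic.

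**Conclusion.** The point holds as a minor efficiency improvement. If site or region is prognostic, the model-based standard error at Week 78 is somewhat too large: a random-site model would bring it down by about 0.6% at ICC 0.02, 1.7 to 1.8% at 0.05 and 4% at 0.10, for 0 to about 1 point of power. Over the assumed ranges, ApoE-by-visit narrows the interval by at most 0.8% and MMSE-by-visit by 0.1% to 2.2%.

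The ceilings in step 2 (2.6% at a 5% share, 5.4% at 10%) should not be read as the expected gain, because they assume perfect balance and full recovery of the site variance. The ICC range, the by-visit effects and the single-visit approximation to the MMRM are all assumptions. The conclusion applies to v1.0 to v3.0; the v4.0 model has still to be checked.

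**What to change.** Check Section 16.2.2.4 of v4.0 and the SAP. If the model is unchanged, then before unblinding:

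- Add region, with countries or sites pooled by a pre-specified rule, as a fixed effect, or site as a random effect, to the CDR-SB, MMSE, ADAS-Cog 13 and ADCS-ADL-MCI models. Do not fit about 150 fixed site effects.
- Add ApoE ε4-by-visit to all four models.
- Add baseline MMSE-by-visit to the CDR-SB, ADAS-Cog 13 and ADCS-ADL-MCI models. The MMSE model already has it.
- If site is still left out, state the reason.

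The cost is a change of wording and a few degrees of freedom out of about 1350 subjects; no new data are needed. The limitation is that region recovers only the between-region part of the site variance, so rater differences between sites within a region stay in the residual. A random site effect recovers more, but adds a variance component to be estimated.

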#### **16.2.2.5. Analysis of the Secondary Endpoints**

##### **16.2.2.5.1. Change From Baseline to Week 78 in MMSE**

The population for the analysis will be subjects in the ITT population with a baseline and at least one post-baseline MMSE value. A MMRM model will be used as the primary analysis to analyze change from baseline MMSE using fixed effects of treatment, time, treatment-by-time interaction, baseline MMSE value, baseline MMSE by time interaction and baseline ApoE  $\epsilon 4$  status.

##### **16.2.2.5.2. Change From Baseline to Week 78 in ADAS-Cog 13**

The population will be subjects in the ITT population with a baseline and at least one post-baseline ADAS-Cog 13 score. An MMRM model will be used as the primary analysis to analyze change from baseline ADAS-Cog 13 using fixed effects of treatment, time, treatment-by-time interaction, baseline ADAS-Cog 13, baseline ADAS-Cog 13 by time interaction, baseline MMSE, and baseline ApoE  $\epsilon 4$  status.

##### **16.2.2.5.3. Change From Baseline to Week 78 in ADCS-ADL-MCI**

The population will be subjects in the ITT population with a baseline and at least one post-baseline ADCS-ADL-MCI score. An MMRM model will be used as the primary analysis to analyze change from baseline ADCS-ADL-MCI using fixed effects of treatment, time, treatment-by-time interaction, baseline ADCS-ADL-MCI, baseline ADCS-ADL-MCI by time interaction, baseline MMSE, and baseline ApoE  $\epsilon 4$  status.

#### **16.2.2.6. Tertiary Endpoints Analysis**

##### **16.2.2.6.1. Placebo-Controlled Period**

Where appropriate, a MMRM model will be used as the primary analysis to analyze change from baseline using fixed effects of treatment, time, treatment by time interaction, baseline value, baseline value by time interaction, baseline MMSE and baseline ApoE  $\epsilon 4$  status.

Otherwise, an analysis of covariance or its non-parametric equivalent may be used to analyze these exploratory endpoints.

CONFIDENTIAL

The information contained herein may not be used, disclosed, or published without the written consent of  
Biogen MA Inc.

#### **16.2.2.6.2. Long-Term Extension Period**

The additional endpoints for the LTE period are change from baseline over the placebo-controlled and LTE periods of the study. Analyses will be presented by treatment group in the placebo-controlled period using the placebo-controlled period baseline. Details of the analyses will be pre-specified in the SAP.

### **16.3. Pharmacokinetics**

#### **16.3.1. Analysis Population**

The population for PK analysis is defined as all subjects who were randomized, were dosed with study treatment, and had at least 1 measurable aducanumab concentration in serum.

#### **16.3.2. Method of Analysis**

The population PK characteristics of aducanumab will be determined by nonlinear mixed effects approach. Covariates that might influence the disposition of aducanumab (e.g., body weight, age, sex, immunogenicity, ApoE  $\epsilon$ 4 status) will be evaluated and the potential exposure-response relationships will be explored.

### **16.4. Safety**

#### **16.4.1. Analysis Population**

The safety population is defined as all subjects who received at least 1 dose of study treatment (including placebo and aducanumab).

#### **16.4.2. Methods of Analysis**

All AEs, laboratory data, ECG, neurological and physical examinations and vital signs will be evaluated for safety.

##### **16.4.2.1. Adverse Events**

Only treatment-emergent adverse events (TEAEs) will be presented in the summary tables. Treatment emergent is defined as having an onset date that is on or after the start of study treatment, or as worsening after the start of study treatment.

Incidence of TEAEs will be summarized by treatment groups, overall, by severity, and by relationship to study treatment for the placebo-controlled period and over the 24-month LTE period. The summary tables will include incidence estimates for overall system organ class as well as for preferred terms within each system organ class. AEs will be coded using the Medical Dictionary for Regulatory Activities (MedDRA).

CONFIDENTIAL

The information contained herein may not be used, disclosed, or published without the written consent of Biogen MA Inc.

#### **16.4.2.2. Clinical Laboratory Results**

Laboratory data will be summarized using shift tables. Shifts from baseline to high/low status for hematology and blood chemistry parameters, and shifts from baseline to high/positive status for urinalysis will be presented. In addition, the shift from baseline to the maximum post-baseline value and the shift from baseline to the minimum post-baseline status will be presented for each laboratory test by treatment group. Also, summaries of laboratory values categorized based on common toxicity criteria grade will be created. Summary statistics for actual values and change from baseline will also be presented for quantitative laboratory data.

#### **16.4.2.3. Vital Signs**

The analysis of vital signs will focus on clinically relevant abnormalities.

#### **16.4.2.4. ECG**

The number and percentage of subjects with shifts to categorical values (abnormal not AE, or abnormal AE) will be summarized by treatment group.

#### **16.4.2.5. Columbia Suicide Severity Rating Scale**

The Columbia Suicide Severity Rating Scale data will be summarized by treatment group.

### **16.5. Immunogenicity Data**

#### **16.5.1. Analysis Population**

The analysis population for immunogenicity is defined as all subjects in the safety population who have at least 1 post-dose sample evaluated for immunogenicity.

#### **16.5.2. Methods of Analysis**

Anti-aducanumab serum antibodies will be summarized using shift tables.

### **16.6. Interim Analyses**

#### **16.6.1. Interim Futility Analysis**

An interim analysis for futility of the primary endpoint will occur after approximately 50% of the subjects have completed the Week 78 Visit (or discontinued). In order to maintain the treatment blind, an independent group external to Biogen that will not be involved in the conduct of the study after unblinding will perform the interim futility analysis. This independent group will present the unblinded interim analysis to the IDMC. The IDMC may recommend terminating the study for futility if it is evident that the efficacy of aducanumab is unlikely to be achieved.

The futility criteria will be discussed in detail in the SAP.

CONFIDENTIAL

The information contained herein may not be used, disclosed, or published without the written consent of Biogen MA Inc.

### **16.6.2. Interim Superiority Analysis**

An interim analysis for superiority may be performed after approximately 50% of the subjects have completed the Week 78 Visit (or discontinued). The Lan-DeMets method with O'Brien-Fleming stopping boundary for efficacy will be used. In order to maintain the treatment blind in the event of this interim analysis, an independent group external to Biogen that will not be involved in the conduct of the study after unblinding will perform the interim superiority analysis. The independent group will present the unblinded interim analysis to the IDMC. The aim of this interim analysis is to allow the possibility to demonstrate treatment effect early. The analysis will be discussed in detail in the SAP.

### **16.7. Sample Size Considerations**

The study's sample size is based, in part, on results from a protocol-specified interim analysis from Study 221AD103 which included 1 year data from 1, 3 and 10 mg/kg treatment groups.

A sample size of 450 subjects per treatment group will have approximately 90% power to detect a true mean difference of 0.5 in change from baseline CDR-SB at Week 78 between the 2 treatment groups. This power calculation is based on a 2-sided t-test assuming equal variance with a final significance level of 0.05, a SD of 1.92 and a drop-out rate of 30%. The SD estimate of 1.92 for Week 78 reflects a 39% increase over the SD from the protocol-specified interim analysis of 1-year data.

The assumed true mean difference of 0.5 between the 2 treatment groups represents an approximately 25% reduction in the placebo mean change from baseline at Week 78 if the placebo mean change is estimated to be 2.

The sample size may be reassessed in a blinded manner approximately 3 months before enrollment is complete if at least 15% of the data are available on the primary endpoint. At this interim time-point, the SD for the primary endpoint will be estimated based on the blinded data. The sample size may be increased if the SD is estimated to be more than approximately 2.07. In addition, the sample size could be increased using external clinical trial results that become available after the start of the study.

CONFIDENTIAL

The information contained herein may not be used, disclosed, or published without the written consent of Biogen MA Inc.

## **17. ETHICAL REQUIREMENTS**

Biogen [REDACTED], and the Investigator must comply with all instructions, regulations, and agreements in this protocol and applicable International Conference on Harmonisation (ICH) and Good Clinical Practice (GCP) guidelines and conduct the study according to local regulations.

The Investigator may delegate responsibilities for study-related tasks where appropriate to individuals sufficiently qualified by education, training, and experience, in accordance with applicable ICH and GCP guidelines. The Investigator should maintain a list of the appropriately qualified persons to whom significant study-related duties have been delegated.

### **17.1. Declaration of Helsinki**

This study will be performed in alignment with the ethical principles outlined in the Declaration of Helsinki.

### **17.2. Ethics Committee/Institutional Review Board**

The Investigator must obtain EC/IRB approval of the protocol, ICF, and other required study documents prior to starting the study. Biogen will submit documents on behalf of the investigational sites worldwide in compliance with local requirements.

If the Investigator makes any changes to the ICF, Biogen must approve the changes before the ICF is submitted to the EC. A copy of the approved ICF must be provided to Biogen. After approval, the ICF must not be altered without the agreement of the relevant EC and Biogen.

It is the responsibility of the Investigator(s) to ensure that all aspects of institutional review are conducted in accordance with current applicable regulations.

Biogen must receive a letter documenting EC/IRB approval, which specifically identifies the protocol, protocol number, and ICF, prior to the initiation of the study. Protocol amendments will be subject to the same requirements as the original protocol.

A progress report must be submitted to the EC/IRB at required intervals and not less than annually.

At the completion or termination of the study, the investigational site must submit a close-out letter to the EC/IRB and Biogen.

